### Potential confounding covariates

Participant age, sex, BMI, maternal educational level, presence of a smoker (who smokes outside, as households with an indoor smoker will be excluded), as well as history of asthma, eczema and allergies will be assessed using the Isaac Questionnaires,(25) as these could be potential confounders of the range hood use and asthma symptom relationship. Geographic factors which could influence the air quality such as proximity of the home to major roadways, railways and industrial sites will be assessed by geocoding the home address of the family. Outdoor PM2.5 and NO2 concentrations will be estimated from regulatory data and/or local low-cost sensor network(s).

# Analysis

## Environmental Assessment and Appliance Use

### Calibration, Initial QA of the Data

We performed multiple sets of instrument co-locations of the e-Lichens air quality monitors for cross calibration, and comparison to reference monitors. Those colocates occurred in June 2021 before any field deployments, in the fall (Oct-Nov) of 2021 and again in June of 2022, after the last field deployment.

Quality assurance of the pollutant data will include:

- Preliminary visual review of data
- Confirm consistent units for temperatures (some of which were recorded in F and some in C)

For quality assurance, thermocouples were tested simultaneously during cooking events to ensure that all showed similar response rates to temperature changes (which they did).

### Compiling, Aligning and QA of Continuous Data

Data will be compiled from our various data collection sources to create a master environment/appliance use dataset for each household in the study. The data include the following:

- Main living area measurements
  - eLichens; 1 min interval measurements (Pull from eLichen API with Python script): NO2, Total VOC, CO2, PM2.5, Temperature, Relative humidity, Sound intensity
  - Ogawa samplers: (Pull from spreadsheet directly to R): Time-integrated NO2 and NOx over periods of roughly 1-week each
- Kitchen measurements (pull from Box uploads directly into R):
  - Burner-adjacent temperature measurements from thermocouples; 1 min interval measurements
  - Temperature above cooktop and at oven outlet, measured by HOBOs; 1 min interval measurements
  - Airflow through hood exhaust, measured by vane anemometer; 1 min interval measurements
- Start and stop times for sampler/data logger deployment (Pull from REDCap download directly to R)
  - Pre-intervention data logging start and stop date/time (end of initial visit-time of Ogawa placement at intervention visit)
  - Post-intervention data logging start and stop date/time (time of new Ogawa placement-removal of Ogawa at final visit)
  - Variables for date of intervention and date of range hood replacement/work
- Outdoor air pollution data
  - PM2.5, NO2 (Pull from regulatory data, create inverse distance weighted surface- may also be able to access data from BEACO2N supplemental, high-resolution network)

Prior to calculating any summary measures, all data will be visually reviewed to screen for obvious quality assurance issues including the following: missing data; instrument malfunction (e.g. values out of range of typical residential conditions); data points that are inconsistent with temporally adjacent values (e.g. a one-minute value of 500 ppb NO2 in the middle of a steady progression from a low baseline to a peak that is below 100 ppb); shifts in baseline values that suggest that the device has not equilibrated after deployment, 1-h time shifts in some but not all data following spring or fall daylight savings time changes; and inconsistencies between temperature sensors at the stovetop and above the stove. Any issues identified and any adjustments (e.g. shifting of one or more time series by 1 hour to fix the time-change error) will be documented.

We will add flags for periods of missing data or data points removed based on the visual screening. When data are missing over short intervals and interpolation based on neighboring data is feasible, interpolated values will be imputed into the dataset using the simplest method that is consistent with the pattern of the surrounding data, and the imputation will be documented. As an example, a single missing data point in a steadily

increasing concentration profile may be estimated by linear interpolation, but an interval of 5 missing data points during a first order decay may be estimated based on the fitted decay. Intervals of missing data that are not clearly interolatable will be left as missing values.

Air quality measurements recorded by the eLichens monitors may be adjusted to achieve consistency across devices, based on analyses of instrument co-locations for cross calibration. Any adjustments will be documented. For situations where multiple devices were present (e.g., duplicate sensors deployed) we will calculate all metrics with each device and average the results by event/metric.

At this point there will be a temporally aligned dataset of all continuous data from each home.

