At the baseline data phone visit, study staff will conduct interviews to complete the baseline questionnaires: the modified ISAAC Core Questionnaire (a four-page questionnaire about asthma and associated diseases), the ISAAC Environmental Questionnaire (a one-page excerpt of a questionnaire regarding environmental exposures at home) and the baseline cooking survey (a two-page Questionnaire about cooking behaviors in the household and some demographic information about the parent). Portions of the ISAAC Core questionnaire assess general medical history (whether a child has ever had symptoms consistent with asthma, allergies or eczema), these questions will be asked of all children. The questions specific to an asthma diagnosis will only be asked of the children with asthma.

HOME VISIT #1:

2 days prior to the home visit an appointment reminder will be sent, with a link to complete the visit surveys to complete via REDCap: the childhood Asthma Control Test (cACT, only if the child has asthma, a one-page symptom questionnaire) and the follow up cooking survey. These surveys should take no more than 5-10 minutes.

This visit will occur at the participant homes. An assessment of the cooking ventilation present in all participant's homes will be performed at the time of the first study visit. This will include verifying that a range hood is present and exhausting to the outdoors. If a hood is present, functional and exhausting to the outdoors, a measurement of the airflow through that hood will be performed by an experienced range hood assessor who is also a licensed contractor. If air flow is less than 100 cfm or noise levels are intolerable (>60 dBA) for settings >100 cfm, the range hood will be replaced with a functioning range hood model during or prior to visit #2. The range hood assessment will be performed in approximately 30 minutes to minimize the duration of this first visit. At the time of this measurement, the contractor will also assess how much work is necessary to replace the range hood in this dwelling and whether it is feasible within the study timeframe and budget.

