If the airflow through the stove hood was deemed inadequate at visit one, this will be replaced by a licensed general contractor (either at home visit 2 or in the period between the home visits 1 and 2), wearing appropriate PPE. The subjects will not be responsible for any expenses associated with installing the range hood, and the general contractor will not have access to any study data other than those data that they access in their usual scope of work (building addresses, building owner contact information, the stove range hood measurements that they perform). If the contractor notes the presence of unsafe conditions that they are unable to remedy (e.g., faulty electrical wiring) or features that would exceed the study budget, stove hood installation will not proceed and participants will be released from the study population. In that case the range hood will be left in, or returned to, the condition it was in at the beginning of the study.

HOME VISIT #2: (approximately 2 weeks after the first home visit)

2 days prior to the visit an appointment reminder will be sent, with links to complete the surveys to complete via REDCap (cACT if the child has asthma and the cooking survey for everyone). This home visit will be performed by one or two study staff members. Upon arrival, the child and their guardian will be asked to complete their surveys on a tablet if they have not already done so.

The child and their guardian will receive the educational intervention. This intervention will be a short video presentation, which the child and their guardian will watch at that time. They will then be provided the link for them to watch the video again at their leisure. Staff will be available to answer any questions they have about the video.

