# Study Methods

## Study Design

This is a before-after trial in homes in the San Francisco Bay Area that have both a school-aged child, a gas stove and a venting range hood or over-the-range microwave and hood (OTR). The trial assessed a cooking ventilation intervention consisting of: (1) ensuring that the home has a working range hood that meets both airflow and sound performance standards and (2) education about the hazards of cooking pollutants and the benefits of using the range hood whenever cooking occurs. The intervention started with measurements of the range hood airflow and sound level. If the existing range hood or OTR did not meet the targeted combination of a minimum airflow of 100 cubic feet per minute (cfm) and sound pressure (loudness) no greater than 60 A-weighted decibels (dBA) at a distance of 2 m, a contractor assessed the feasibility of replacing the device. When feasible, the participant (and building owner, if the participant was a renter) was offered a replacement hood or OTR that met the specifications. All study participants received education regarding use of the range hood during all cooking events. We installed stove and range hood sensors in participant homes for the entire data collection period, allowing for objective measurements of cooking intervals and range hood use both before and after the intervention. In addition to a working range hood, we provided all families an incentive at each visit (totaling \$100 per family). Outcomes include measurements of estimated PM2.5 and NO2 in the household, and both objective and subjective measures of respiratory health in the children (spirometry, FeNO, ISAAC Asthma questionnaire and ISAAC Environmental Questionnaire for all children; the asthma control test as well for children with asthma). The trial is registered with clinicaltrials.gov, #NCT04464720.

[figure not shown]

Figure 1. Study Diagram

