### Visit #2

The parent and child completed the same pre-visit surveys, and at the visit the child performed the same lung function testing. They were given the educational intervention, consisting of watching the video and receiving a reminder card and magnet. The equipment in place at the home was checked (anemometer, thermocouples, eLichens). The Ogawa passive sampler was exchanged for a new one. If air flow in the range hood (or OTR) was less than 100 cfm or noise levels are intolerable (>60 dBA) for settings >100 cfm, the range hood was

replaced with a functioning range hood model during or prior to this visit, if feasible within the study timeframe and budget.

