  - Peaks that occur within 10 min of each other (also an imprecise threshold based on experience of the research team), with intervening concentrations not dropping to <50% of the level of the first peak, shall be considered as being part of the same event.
  - Determine an event baseline based on the fitted baseline / background.
  - Events for which algorithmic classification provides nonsensical or undetermined results will be flagged and evaluated visually by at least two researchers.

For each pollutant event (PM2.5, NO2, CO2), we will calculate the following statistics:

- Event statistics:
  - start time and end time of *increasing* concentrations (i.e., not including the decay)
  - duration of emissions event
  - time of return to baseline (based on fitted baseline)
  - end of decay interval.
- Pollutant statistics:
  - prominence (highest ten-minute average above baseline) of each pollutant
  - integrated concentration of each pollutant above baseline (ug/m^3-min)

Notes:

- There should be few or no NO2 events that are not linked to cooking.
- There are unlikely to be any sharp CO2 events not linked to cooking; but there will be CO2 events linked to occupancy.
- There could be many PM2.5 events not linked to cooking.

All events identified by algorithms (Burners, cooking, range hood, PM2.5, NO2, CO2 increases) will be visually reviewed and any that are not deemed to be clearly correct will be reviewed and discussed with a second researcher.

Calculate Summary Statistics for each home during each of the pre- and post-intervention periods:

- Primary summary statistics of cooking and range hood events
  - Number of discrete events of individual burner use (confirmed and confirmed + possible) for cooktops, ovens, and any burner.
  - Number of cooking events.
  - Number and fraction of cooking events with substantial particle emissions.
  - Total burner minutes.
  - Mean (SD) number of burners used and burner minutes per cooking event (as an indicator of similarity).
  - Delay from start of cooking to start of range hood use.
  - Fraction of total burner minutes that reflects usage of the front burners and fraction that reflects usage of the back burners.
  - Fraction of cooking events with any range hood use.
  - Fraction of cooking events with range hood used for >80% of cooking burner use.

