## Analysis Methods

**Determine if a cooking ventilation intervention (not receiving anything, receiving education only, or receiving education and range hood replacement) is associated with changes in (1) ventilation, (2) front vs back burner use, (3) household particulate matter, (4) NO2 and (5) CO2 levels.** We will use a

Wilcoxon Signed Rank test to compare the pre-intervention data to the post-intervention data to assess the relationship between intervention status and the following variables.

1. Range hood use, characterized 4 ways:

- fraction of cooking events with any range hood use (this will be primarily estimated using the vane anemometer data, but can also be assessed with self-reported (weekly) range hood use frequency)
- fraction of cooking events with  $\geq 80\%$  range hood use
- fraction of cooking-linked pollutant events with substantial range hood use
- mean delay between start of cooking and start of range hood use

2. Front versus back burner use, characterized 2 ways

- fraction of total burner minutes that reflects usage of the front burners and fraction that reflects usage of the back burners.
- self-reported most common burner use

[figure not shown]
3. PM2.5 levels, characterized four ways:

- mean prominence (increase above baseline) of PM2.5 during cooking-linked pollutant events
- mean ug/m^3-min PM2.5 aggregated during cooking-linked pollutant events
- total magnitude of emissions (aggregated PM2.5 during cooking-linked pollutant events divided by burner minutes)
- time-integrated PM2.5 (if discernible from the data)

4. Nitrogen dioxide levels, characterized four ways:

- mean prominence (increase above baseline) of NO2 during cooking-linked pollutant events
- mean ppb-min NO2 aggregated during cooking-linked pollutant events
- total magnitude of emissions (aggregated NO2 during cooking-linked pollutant events divided by burner minutes)
- time-integrated NO2

5. Mean prominence of carbon dioxide during cooking-linked pollutant events

In general, the covariates that will vary over time (eg. total burner use minutes) are not related to the intervention status and thus do not need to be controlled in order to prevent bias.

Given the small final sample size, these will not be adjusted in the analysis (but original DAG maintained for completeness).

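### The baseline window runs to the intervention visit and ignores the recorded hood-replacement date, so a home whose hood was replaced earlier counts new-hood days as baseline

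*SAP*

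**What the plan says.** The SAP's Study Design section describes a two-part intervention. The first part is "ensuring that the home has a working range hood that meets both airflow and sound performance standards"; the second is education, which is given at visit 2.

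The documents allow the first part to come before the second:

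- Protocol section 9a, Home Visit #1: if the hood fails the targets, "the range hood will be replaced with a functioning range hood model during or prior to visit #2".
- Protocol section 9a, Contractor: the work is done "either at home visit 2 or in the period between the home visits 1 and 2".
- SAP, Visit #2: a failing hood was "replaced with a functioning range hood model during or prior to this visit, if feasible within the study timeframe and budget".

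The opening design paragraph of Protocol section 9a reads differently. It places both education and any replacement after about two weeks of baseline data.

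The SAP's list of data to compile gives the baseline period as "Pre-intervention data logging start and stop date/time (end of initial visit-time of Ogawa placement at intervention visit". The post period starts when the new Ogawa sampler is set out at that visit. The same list includes "Variables for date of intervention and date of range hood replacement/work". The SAP then instructs: "Calculate Summary Statistics for each home during each of the pre- and post-intervention periods". Analysis Methods names three intervention states, "not receiving anything, receiving education only, or receiving education and range hood replacement", and compares pre with post by Wilcoxon signed rank tests.

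**The concern.** A home with a new hood and no education yet fits none of the three states in Analysis Methods. The window definition nevertheless places those days in the baseline. The signed rank test compares one pre value with one post value per home, so it cannot represent a change of hood within the pre period.

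In an early-replaced home, three kinds of baseline data can be affected: the continuous pollutant and appliance data, the Ogawa sample that spans the replacement, and the lung tests done at the intervention visit. If the new hood lowers exposure, as the trial assumes, the PM2.5, NO2 and CO2 contrasts for that home move toward no effect, and the lung contrast may do so too.

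The direction for hood use and burner position is not established. Protocol section 9a has anemometers moved to new hoods after the intervention. That can be read either way on whether airflow was being logged on an early-installed hood before visit 2.

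With 14 homes, a study that calls itself underpowered, and a Framework section that reports p-values because the tests give no estimate, a reader could not see this dilution in the results.

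**Working it through.** **Is the replacement date used anywhere?** Each SAP section that could use it was checked.

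| SAP section | What it does | Uses the replacement date? |
|---|---|---|
| Analysis Populations | Requires 3 or more cooking events before and after the intervention; for lung outcomes, tests before and after | No |
| Summary statistics for each home | Computes values by pre and post period | No |
| Analysis Methods | Unadjusted signed rank tests, pre against post | No |
| Sensitivity Analyses | Number of visits; removal of two homes whose indicated replacement was not received; asthma subgroup | No |
| Missing Data | Regression prediction for correlated exposure data, otherwise complete case | No |

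The removal of two homes concerns replacements that were not made. It does not touch the timing of those that were.

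**How many homes could be affected?** The SAP lists 2 + 5 + 7 = 14 homes. Two had a replacement indicated but not received, so at most 14 − 2 = 12 could have been replaced early. The documents do not say how many hoods failed or were replaced, so 12 is only a ceiling and the lower limit is 0.

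**How much of one home's baseline could be affected?** The share of baseline days with the new hood is k/L. Here L is the number of days from first visit to education (SAP Study Design: range 5 to 26, mean 13.1), and k is the number of days from replacement to the intervention visit. The documents do not give k, so the values below are assumptions.

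| Assumed k (days) | L = 13.1 | L = 26 |
|---|---|---|
| 1 | 1/13.1 = 8% | 1/26 = 4% |
| 3 | 3/13.1 = 23% | 3/26 = 12% |
| 7 | 7/13.1 = 53% | 7/26 = 27% |

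In the shortest window (L = 5) the share is 1/5 = 20% for one day and 3/5 = 60% for three.

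If cooking events are spread evenly over the window and the hood's effect is constant, a per-event mean keeps a fraction 1 − k/L of the hood part of the contrast. At L = 13.1 that is 77% for k = 3 and 47% for k = 7. In practice, event-based outcomes depend on the share of cooking events or burner minutes after the replacement, which is not given. The effect on the signed rank p-values cannot be computed from the documents.

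**Can the data be split afterwards?** The continuous series can be, because the date is recorded. In a three-visit home the single baseline Ogawa sample cannot. The two four-visit homes had one extra visit before the intervention and may have a separate sample taken wholly before the replacement.

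**How small can a subset be and still be tested?** With no ties or zeros, the smallest exact two-sided signed rank p-value is 2/2^n. For n = 5 it is 2/32 = 0.0625; for n = 6 it is 2/64 = 0.031. With five or fewer homes, p < 0.05 cannot be reached.

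**The case against.** The strongest reply is that no early replacement is documented. The passages permit it but none says it happened, and both the opening design paragraph and the anemometer sentence in Protocol section 9a fit replacement at visit 2. This stands as a limit on size: the count may be zero. It does not supply the missing rule, and a reader of the SAP cannot check the count.

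A second reply is that the quoted window sits in an inventory of data sources and is not labelled as an analysis definition. That is true, but it is the only definition of the periods in either document. The point is weaker for lung outcomes, where Analysis Populations says only before and after the intervention, and no rule says which test is the pre value when a child was also tested at visit 1.

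A third reply is that a hood acts only when it is run, and the education on running it comes at visit 2, so the hood-only effect could be small. The education part of the contrast is indeed untouched, and any dilution of the pollutant contrasts is unlikely to create a false positive. Small is still not zero, and the SAP counts the hood as part of the intervention.

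The lead times are assumed, and the pooled mean of 13.1 days mixes schedules: in a home with about one week between visits, a 7-day lead would fill the whole window. The percentages are therefore illustrations, not estimates.

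Finally, the recorded date covers hood work as well as replacement, so cutting there might discard some valid baseline. Work that brings a hood up to target is itself the first part of the intervention, so the cut is defensible.

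**Conclusion.** The concern holds. Followed as written, the plan counts new-hood days as baseline in any home whose hood was replaced before the intervention visit, although the date needed to avoid this is compiled. The omission is certain; its size is unknown. Between 0 and 12 of 14 homes could be affected, and with none there is no bias. The pull toward no effect on pollutant outcomes rests on the assumption that the new hood lowers exposure before education is given. This should be fixed, because the check is cheap and the results cannot be read properly without it.

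**What to change.** Report how many hoods were replaced before the intervention visit and by how many days. If none were, one sentence saying so closes the point. Reconcile the passages on replacement timing, and state whether the anemometer was logging on the new hood between an early replacement and the intervention visit.

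If any hood was replaced early, keep the present split as the main analysis, because the revision notes show that processing was done and analyses were being completed. Add two sensitivity analyses, labelled as a late change:

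- **Continuous-data outcomes:** end the baseline at the earlier of the recorded hood work and the education visit, and leave the days between out of both windows.
- **Ogawa and lung outcomes:** exclude early-replaced homes, except that a home with a separate Ogawa sample taken wholly before the replacement can use it. Do not substitute first-visit lung tests in those homes only: Outcome Definitions says these were added later so that children could learn the techniques. Show results descriptively if fewer than 6 homes remain.

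The cost is SAP wording, a count from a date already recorded, and recomputed summaries and tests for the sensitivity analyses. The downside is some lost baseline days, possibly a home falling below 3 baseline cooking events, and fewer homes in the Ogawa and lung comparisons.
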